6.2.2.8 Sensitivity Analysis 2: Per-protocol Analysis in Confirmed Cases of Mid-Q LBBB

A second sensitivity analysis will be performed to analyze the per-protocol effect of the treatment upon the CCS at 6 months, in the subset of subjects treated per-protocol (i.e., in the per-protocol cohort defined in section 6.1.3). This second sensitivity analysis will proceed in the same manner as the main (ITT) analysis of the primary endpoint, with a chi-square test being used for the comparison of interest. Example SAS code is as follows:

```
*** Primary objective - sensitivity analysis #2;
proc freq data = analysis.PrimaryObj;
where perProtocol = 1;
table aCRT_act*CCS_Improved/nocol nopercnt chisq;
run;
```

6.2.2.9 Sensitivity Analysis 3: Effect from Out of Window Visits

As stated in the CIP, data analyses include follow-up visits, regardless of whether the visit occurs within the window. However, in the presence of many subjects having late visits, the classification of the primary endpoint as a 6-month outcome becomes less accurate. Therefore, a description of visit compliance and a summary of actual days to 6 month assessments will be performed by treatment group. If a Wilcoxon test shows an imbalance in days from randomization to 6 month assessments between aCRT ON and aCRT OFF, or if > 20% of subjects from either study arm have late 6-month visits, one further sensitivity analysis will be performed. In this analysis, CCS will be calculated as above, except that for subjects who have 6 month visits occurring after the visit window has closed (i.e., 224 or more days after randomization), the NYHA and Global Assessment scores used in determining CCS will be carried forward from the baseline or 3 month visit, as available. If a subject's 6 month visit is late and out of window, and they have no post-randomization NYHA or Global Assessment Score data to carry forward, they will be assigned a score of "Unchanged" in the absence of any events that would lead to them being classified as "Worsened". This sensitivity analysis will mirror the main ITT analysis, with ITT assignments for treatment, and using a Chi-square test with two-sided alpha = 0.05 to determine whether the alternative formulation of CCS is associated with treatment, as exemplified in the following SAS code:

```
*** Primary objective - sensitivity analysis #3;
proc freq data = analysis.PrimaryObj;
table aCRT_ITT*CCS_Improved_inWind/nocol nopercnt chisq;
run;
```

Differences observed between this analysis and the main ITT analysis of the primary endpoint can provide evidence about the main endpoint's sensitivity to being measured within the protocol-defined visit windows.

6.2.3 Secondary Objective #1: Change in NYHA Class at 6 and 12 Months

Secondary objective #1 is to test the hypothesis that the odds of being in a higher NYHA class is different in the aCRT ON compared to those in the aCRT OFF group.

6.2.3.1 Hypothesis

Let NYHA class be an ordinal variable with a multinomial distribution. The odds ratio (OR) for being in the next higher stratum for aCRT ON versus aCRT OFF will be tested. The null and alternative hypotheses are:

$$H_0 : OR = 1$$

$$H_a : OR \neq 1$$

6.2.3.2 Analysis Methods

NYHA class is an ordinal variable with higher classes indicating a worse degree of heart failure. NYHA class will be collected at baseline and at the 3, 6, and 12-month follow-up visits. NYHA class at follow-up assessments (hence excluding the baseline in the outcome variable) will be analyzed with a proportional odds logistic regression model that will account for the correlation of repeated assessments within each subject. The treatment arm allocation will be included as a main effect. The baseline NYHA class and time will also be included in the model as fixed covariates. Example SAS code is shown below:

```
*** Secondary objective #1: Change in NYHA class;
proc sort data = analysis.secObj1;
by PT t;
run;
proc glimmix data=analysis.secObj1;
class PT aCRT_ITT NYHA_base t;
model NYHA = aCRT_ITT NYHA_base t/ dist=multinomial link=cumlogit solution;
random intercept / subject=PT type = ar(1);
run;
```

The proportional odds assumption will be assessed graphically using methods described in Harrell, 2001 with an outline and proprietary R code provided under separate cover. The assessment of whether the assumption is justified, given the observed effects, will be left to the statistician conducting the analysis. Should the assumptions underlying the proportional odds model seem insufficiently justified after this investigation, modifications to the general form may be made, including fitting a partial proportional odds model or collapsing the outcome variable to allow for a simpler logistic regression model with a binary response. An alternative specification (for example, collapsing levels of NYHA by grouping classes III/IV/V together and classes I and II together, and then using a standard binary response logistic regression) will also be considered should fewer than 5 subjects with NYHA > 3 exist in one of the two treatment arms at 6 or 12 months.

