6.2.2.7 Sensitivity Analysis 1: Adjusting for Subject Gender and NYHA

To test the potential effect of differential distribution of NYHA class and subject sex among treatment groups, a sensitivity analysis will be done using a logistic regression model with randomization arm, gender and NYHA class as fixed effects, and site as the random effect. Sites with a low number of enrollments will be grouped into clusters according to methods outlined in section 6.3 (Center Pooling) below. Example SAS code is as follows:

```
proc glimmix data=analysis.secObj1;
class aCRT_ITT NYHA Sex site;
model CCS_Improved = aCRT_ITT NYHA Sex/ dist=bin link=logit solution;
random intercept / subject=site type = vc;
run;
```

It is noted that, under ideal circumstances, the p-value based on the resulting score test would be used in this case, as that is the direct analog to the chi-square test in the ITT analysis, rather than the more powerful test based on the Wald estimator provided by Proc Glimmix in SAS (see sample size simulations available under separate cover). Should Proc Glimmix fail to converge on parameter estimates, the equivalent model specification will be fit using the nlme package in R. If that also fails to converge, a conditional logistic regression model will be used instead (i.e., SAS Proc Logistic with site

specified in a strata statement). This sensitivity analysis will be performed in the ITT dataset; subjects who cross over and subjects treated in violation of major inclusion/exclusion criteria will still be analyzed according to their assigned randomization.

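### SAP 6.2.3.2: the AR(1) option in the NYHA model code has no effect on a single random intercept, and leaving the estimation method at its default shrinks the reported odds ratio toward 1

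*SAP*

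**What the plan says.** SAP 6.2.3.1 defines the quantity of interest: "The odds ratio (OR) for being in the next higher stratum for aCRT ON versus aCRT OFF will be tested". The test is two-sided against OR = 1.

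SAP 6.2.3.2 plans a "proportional odds logistic regression model that will account for the correlation of repeated assessments within each subject". "NYHA class will be collected at baseline and at the 3, 6, and 12-month follow-up visits", and baseline enters as a covariate, so each patient contributes at most three outcome readings. Under SAP 6.2.1 and 6.2.3.4 a deceased patient is given class V, which makes five levels.

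The prose names no correlation structure, estimation method or response order. Those choices appear only in the code, introduced by "Example SAS code is shown below":

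- procedure line: "proc glimmix data=analysis.secObj1", with no METHOD= option;
- model line: "model NYHA = aCRT_ITT NYHA_base t/ dist=multinomial link=cumlogit solution", with no response-order option;
- random line: "random intercept / subject=PT type = ar(1", closing bracket omitted here.

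The treatment variable is on the CLASS statement with no reference level. For comparison, the site-level intercept in SAP 6.2.2.7 is coded "random intercept / subject=site type = vc".

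SAP 6.2.1 commits to reporting absolute and relative effect sizes where applicable.

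**The concern.** The code asks for serial correlation in a place that cannot hold it. Sorting by patient and time and then requesting AR(1) suggests that a correlation decaying with the gap between visits was intended. A single intercept cannot provide that.

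The second issue affects the result that will be published. Linearised pseudo-likelihood is known to underestimate random-effect variances and conditional effects when each cluster has few categorical readings. Three ordinal readings per patient is such a case. The NYHA odds ratio is a deliverable as well as its p-value, so a predictable pull toward 1 would understate any effect of aCRT in either direction and shift the confidence interval with it.

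Third, the code does not settle whether the printed coefficient is the odds ratio of 6.2.3.1 or its reciprocal.

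**Working it through.** **Plan's own figure.** The documents state no sample size, power or expected odds ratio for this objective. The 220 randomized patients were sized for the Clinical Composite Score. With 3% crossover each way the rates are 0.97×0.75 + 0.03×0.55 = 0.744 and 0.97×0.55 + 0.03×0.75 = 0.556. At 110 per arm an uncorrected chi-square test then has 83.7% power, consistent with the SAP's target of more than 80%. That calculation is unaffected by this point; 220 is used below only as an input.

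**AR(1) on one intercept.** An AR(1) covariance matrix has elements σ²ρ^|j−k|. With one random effect per patient, j = k = 1, so the matrix is the single number σ²ρ⁰ = σ². The lag parameter ρ does not enter the likelihood and is not identified. The latent correlation between any two visits is σ²/(σ² + π²/3), with π²/3 = 3.29, whatever their spacing:

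- SD 1: 1/4.29 = 0.23
- SD 2: 4/7.29 = 0.55
- SD 3: 9/12.29 = 0.73

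**Estimation method.** Inputs from the documents: 110 patients per arm, visits at 3, 6 and 12 months, five outcome levels, and the 55% class III / 45% class II baseline mix of protocol 12.4.2. Assumptions not in the documents: between-patient SD of 1, 2 or 3 on the logit scale, a true conditional odds ratio of 0.50 (log −0.693), and the thresholds, baseline effect and time effects. No visits were missing, and class V was not treated as absorbing. Each of 200 data sets per setting was fitted by residual pseudo-likelihood (programmed outside SAS) and by maximum likelihood with 30-point Gauss–Hermite quadrature.

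| SD | Log OR, pseudo-lik. | Log OR, quadrature | Ratio | OR, pseudo-lik. | OR, quadrature | Estimated SD (pseudo / quad.) | Rejection rate (pseudo / quad.) |
|---|---|---|---|---|---|---|---|
| 1 | −0.666 | −0.703 | 0.947 | 0.514 | 0.495 | 0.95 / 0.99 | 94.5% / 96.0% |
| 2 | −0.613 | −0.698 | 0.878 | 0.542 | 0.497 | 1.76 / 2.01 | 57.0% / 60.0% |
| 3 | −0.567 | −0.698 | 0.813 | 0.567 | 0.498 | 2.43 / 3.00 | 33.5% / 35.5% |

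On the same data sets, the log odds ratio is therefore 5%, 12% and 19% smaller than by quadrature. Against the true −0.693 the shortfall is 4%, 12% and 18%. The Monte Carlo standard errors of the pseudo-likelihood means are 0.013, 0.019 and 0.025. The power loss is 1.5, 3.0 and 2.0 points.

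A separate simulation, with log odds ratio −0.9 and 110 data sets per setting, gave ratios of 0.850/0.957 = 0.89, 0.785/0.926 = 0.85 and 0.706/0.869 = 0.81 at SD 1.5, 2.0 and 2.5. These point the same way. Its quadrature mean at SD 1.5 overshoots the true value, so only the ratios on common data sets are used here.

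**Under the null** (600 data sets, SD 2), pseudo-likelihood gave a mean odds ratio of 1.00 and type I error of 3.7%. When the data followed a latent AR(1) process with ρ = 0.8 and the intercept-only model was fitted, the figures were 1.00 and 5.8%. The Monte Carlo standard error at 5% is √(0.05×0.95/600) = 0.9 points, so both are compatible with the nominal level.

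**Direction.** By default the cumulative logit models the lower-ordered classes, and the last sorted level of a CLASS variable is the reference. If the treatment variable is coded 0/1 or OFF/ON, the reference is ON. The printed coefficient is then log[odds(lower | OFF) / odds(lower | ON)], which equals log[odds(higher | ON) / odds(higher | OFF)]. The two reversals cancel. Under a coding that sorts ON first they do not. The SAP does not give the coding.

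**The case against.** The strongest reply is that little of consequence changes. The code is labelled an example and serves a secondary objective. The prose promises only to account for within-patient correlation, and a random intercept does so. The stated hypothesis is a test of OR = 1, the Hommel procedure in SAP 6.5 works on p-values, and the test barely moves. The amount of shrinkage rests on an SD that the documents do not give, and at SD 1 it is small. The SAP also does not say whether its odds ratio is patient-specific or population-averaged, and the attenuation is measured against the former. The defaults described here are properties of the software; the SAP shows only that the options are absent.

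Most of this stands, and it limits the point to the estimate. It does not remove it. The example is the only place where the correlation structure and model options are specified, so an analyst or validator would follow it. The modelling changes that 6.2.3.2 allows concern the proportional-odds assumption and sparse classes, not the estimation method. A random-intercept model estimates a patient-specific odds ratio, so that is the right yardstick for this code.

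A reader might also infer that the output will be the reciprocal of the odds ratio in 6.2.3.1. The documents do not support that: under either natural coding the code already gives the stated direction, and a two-sided test does not depend on it. Nor do they support the inference that AR(1) leaves within-patient correlation unmodelled or makes the fit fail. The option is inert, and no convergence failure has been shown.

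**Conclusion.** The point holds as a modest correction to the specification of secondary objective #1.

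That AR(1) has no effect here is algebra and needs no data assumption. The shrinkage depends on the default being linearised pseudo-likelihood and on the between-patient SD. For an assumed SD of 1 to 3 and a true odds ratio of 0.50, the reported odds ratio would be about 0.51 to 0.57, and its confidence interval would be centred there. Deaths as an absorbing class and missed visits were not modelled.

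The test of OR = 1, the primary analysis and the sample size are not called into question. The direction of the odds ratio is unspecified, which is different from being wrong.

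**What to change.** In the code of SAP 6.2.3.2:

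- add `method=quad` (or `method=laplace`) to the procedure line, and name the method in the prose;
- replace the random line with `random intercept / subject=PT;`, without TYPE=AR(1);
- set aCRT OFF as the reference level of the treatment variable **and** write the response as `NYHA(descending)`. The output is then the odds of a higher class for ON versus OFF, as 6.2.3.1 defines. Descending order alone should not be added: with ON as the default reference it would invert the odds ratio;
- state in one sentence that the odds ratio is patient-specific and that values below 1 favour aCRT ON.

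If serial correlation is wanted, it has to be placed on visit-level effects and must allow for the unequal spacing of 3, 6 and 12 months.

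The cost is a few code options, a sentence or two of text and a slightly longer run time. Making the change before outcomes are examined by arm avoids a departure that SAP 6.8 would require the final report to explain.

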6.2.3.3 Determination of Subjects

The comparison of NYHA class by treatment group will be an ITT analysis.

6.2.3.4 Missing Data

It is expected that the primary cause of missing or unobserved NYHA values in this study will be due to death. As mentioned in section 6.2.1, the NYHA value will be set to class V for deceased subjects. Values at follow-ups that are unobserved for reasons other than mortality will be assumed to be Missing Completely At Random (MCAR) and will be excluded from the analysis; this assumption may be revisited if post-randomization attrition is unexpectedly high. As with the analysis of the primary objective, any subjects missing a NYHA class value at baseline will be assumed to be starting the study with NYHA class II.

6.2.4 Secondary Objective #2: Heart Failure Hospitalizations

6.2.4.1 Hypothesis

The hypothesis tested per secondary objective #2 is that the risk of Heart Failure (HF) hospitalization is lower for subjects randomized to aCRT ON as compared to subjects randomized to aCRT OFF. The null hypothesis is that the hazard for HF hospitalization is the same in both groups, and it will be tested against the two-sided alternative that the hazard differs between groups as follows:

$$H_0: HR_{HF} = 1$$

$$H_a: HR_{HF} \neq 1$$

where HR_{HF} is the hazard ratio in the aCRT ON group vs. the aCRT OFF group.

6.2.4.2 Analysis Methods

This analysis will investigate the effect of treatment group upon the time to first hospitalization for HF after randomization. Subsequent HF hospitalizations for a subject will be ignored for this objective. The risk of HF hospitalization during the 12 months after randomization will be assessed using a Cox proportional hazards regression model, with randomized group as a predictor variable. NYHA class and sex will also be included as covariates to partially account for informative censoring from the competing risk of death.

```
/*Secondary objective #2*/
proc phreg data = analysis.secObj2;
class aCRT_ITT;
model HFhospDays*HFhosp(0) = aCRT_ITT NYHA Sex/r1 ties=exact;
hazardratio aCRT_ITT;
run;
```

A graphical comparison of the incidence of first HF Hospitalization will be made using plots of cumulative incidence functions in the aCRT ON and aCRT OFF groups with mortality as competing risk.

6.2.4.3 Determination of Subjects

The hypothesis test for differing risks of HF hospitalization by treatment group will be an ITT analysis.

6.2.4.4 Missing Data

A very high rate of capture for HF hospitalizations is expected for this study. It is noted that the risk of undercounting (i.e., sites failing to report a HF hospitalization event) is much higher than overcounting (reporting an event as an HF hospitalization when it does not, in actuality, meet the protocol-defined criteria). However, it is unclear why the rate of HF hospitalization misclassification would differ between randomization groups, and the simplifying assumption will be made that false positives and false negatives occur independently of treatment. It is acknowledged that censoring of HF hospitalizations may be informative due to the competing risk of death, with higher mortality rates and larger effects of aCRT upon mortality leading to greater distortions in parameter estimates for this objective. Given expected event rates, a sensitivity analysis will be performed to estimate the effect of one possible informative censoring regime, and is described below in section 6.2.4.5. The sensitivity analysis will be foregone in the presence of very low mortality rates (<=5 deaths in both treatment arms combined) as it is less likely that censoring will be informative in that scenario. If both mortality and HF hospitalization rates are very low, informative censoring from mortality may exert more of an influence on the hazard estimates, but the sensitivity will still be regarded as optional in that situation as the type II error rate of the analysis will be high under any imputation plan.

6.2.4.5 Sensitivity Analysis: Informative Censoring of HF Hospitalization Due to Mortality

In the Adaptive CRT study, 31/478 subjects (6.5%) died within 365 days of randomization. These subjects combined for 21 first hospitalizations in 15.4 subject-years. Under the strong assumption that all deceased subjects would have experienced a hospitalization for HF had they survived at least 365 days after randomization, an additional 10 events would have been observed. Given a similar set of event rates, the Mid-Q Response study can expect 14.3 deaths, with 9.5 observed HF hospitalizations, and up to 5.8 unobserved first HF hospitalizations in the affected subjects. The sensitivity to unobserved events in deceased subjects will be assessed by creating an alternate outcome variable which copies observed HF events, in which all subjects from the study arm with the higher death rate who experience mortality on day t (for all times $t < 365$ days) are assigned a HF event on day $t + 1$. This outcome will have a slightly higher event rate compared to its complete cases equivalent, and will then be substituted its place into the Cox regression model specified in section 6.2.4.2. If the treatment effect is associated with time to first HF hospitalization (i.e., if $p < 0.05$) in the sensitivity analysis but not in the complete cases analysis, or vice versa, then the results of both will be presented together. In this situation, a further sensitivity analysis involving a less extreme assumption about unobserved events (for instance, if only CV deaths would have had an associated HF hospitalization) may be performed as well. In the event the sensitivity analysis does not lead to a different conclusion regarding the effect of aCRT ON upon HF hospitalization, only the complete cases analysis will be presented as part of the objective, and the sensitivity analysis may be referenced and presented in an appendix to the final report.

6.2.5 Secondary Objective #3: All-cause and CV Mortality

The third secondary objective is to test two hypotheses about differences in (A) all-cause mortality and (B) mortality only from CV causes, between subjects randomized to aCRT ON and subjects randomized to aCRT OFF.

6.2.5.1 Hypothesis

The first hypothesis tested per this objective is that the proportion of subjects dying from any cause 365 days or less after randomization is different in subjects with aCRT ON compared to subjects with aCRT OFF. The following hypothesis will be tested in a two-sided test with $\alpha = 0.05$:

$$H_0: \pi_{On} = \pi_{Off}$$

$$H_a: \pi_{On} \neq \pi_{Off}$$

where π_{On} and π_{Off} are the Kaplan-Meier estimates of all-cause mortality in the intention-to-treat aCRT ON and aCRT OFF groups, respectively.

6.2.5.2 Analysis Methods for All-cause Mortality Comparison

The probability of a subject surviving for 365 days past randomization will be estimated using Kaplan-Meier methods. A two-sided 95% log-log confidence interval will be constructed, using Greenwood's formula to approximate the standard error. A log-rank test will be used to assess whether mortality differs between aCRT ON and aCRT OFF groups. This can be accomplished in SAS using code such as the following:

```
proc lifetest data = analysis.secObj3 plots =survival(atrisk failure) outsurv = kmout;
  time SurvivalDays*Death(0);
  survival conftype = loglog;
  strata aCRT_ITT;
run;
```

Subjects will be censored at the last date of study contact (randomization, scheduled or unscheduled visits, termination/study exit date, AE or HCU event dates, or system modification dates) or at day 365 post-randomization, whichever comes first.

6.2.5.3 Determination of Subjects for All-cause Mortality Comparison

The comparison of all-cause mortality will be an ITT analysis.

6.2.5.4 Hypothesis

The second hypothesis to be tested for this objective is:

$$H_0: HR_{CV} = 1$$

$$H_a: HR_{CV} \neq 1$$

where HR_{CV} is the hazard ratio for cardiovascular-related mortality in the (ITT) aCRT ON group compared to the aCRT OFF group.

6.2.5.5 Analysis methods for CV-related Mortality Comparison

Medtronic safety personnel will classify each death per definitions in section 10.3.2 of the CIP as being a cardiac death (or otherwise), a sudden death (or otherwise), or unknown. An effort to sparingly categorize deaths as unknown will be made and that grouping will be reserved for cases only when there is insufficient information to classify. The CIP uses the term cardiac death to refer to "A death related to the electrical or mechanical dysfunction of the heart", but frames secondary objective #3 in terms of characterizing "cardiovascular mortality". For purposes of this SAP, this endpoint includes all cardiac deaths as well as any cardiovascular deaths that are not directly a result of mechanical or electrical heart dysfunction (for example, stroke or embolism).

Subjects will be censored at the last date of study contact (randomization, scheduled or unscheduled visits, termination/study exit date, AE or HCU event dates, or system modification dates), upon death from all other competing (non-cardiovascular) causes, or at day 365 post-randomization, whichever comes first. The probability of cardiovascular (CV) mortality within 365 days of randomization will be modeled using Cox proportional hazards regression. The model may be fit in SAS using the following code:

```
/*Secondary objective #3b*/  
|proc phreg data = analysis.secObj3;  
|  class aCRT_ITT;  
|  model CVdeathDays*CVdeath(0) = aCRT_ITT/r1 ties=exact;  
|  hazardratio aCRT_ITT;  
|run;
```

Additionally, a graphical representation of the CIF for CV mortality, along with the competing risk of non-CV mortality, will be displayed by group.

